## 4. ANALYSIS AND REPORTING

### 4.1 Interim Analysis

An interim analysis will be performed when approximately 50% of the initially planned enrollment is evaluable for efficacy assessments. This interim analysis will be performed by an unblinded team separate from the team responsible for the conduct and analysis of the study. An Independent Data Monitoring Committee (IDMC) will review the data and recommend to the Sponsor to increase the sample size by a fixed amount, keep the current sample size and continue, or stop the study early for futility in the event the conditional power is <20%. If the IDMC recommends an increase in sample size, the maximum increase will be limited to 120 additional participants in blocks of 10 participants. If the conditional power is at or over 85% with the current sample size, then the IDMC will recommend continuing at the current sample size; if it is between 20% and <85%, the IDMC will recommend increasing the sample size. The increase will be chosen with the goal of increasing the sample size by the minimum number of subjects sufficient to raise the conditional power to at least 90%. If the conditional power at the current sample size is over 20% and the maximum increase of 120 subjects falls short of raising the conditional power to at least 90%, the committee will recommend an increase of 120 subjects. No further information will be provided to the sponsor beyond this recommendation.

The interim analysis will be conducted approximately 16 weeks after randomization of approximately 125 participants, i.e. when approximately 50% of the initially planned participant enrollment (250) is evaluable for efficacy assessments (approximately 12 weeks); and related data cleaning, database freeze, and administrative tasks have been completed on this cohort (approximately 4 weeks).

In case the study is stopped early for futility, participants will be managed according to a study termination plan.

In the case of an early stop for futility, initial results may be released prior to full database lock; however, clinical study report (CSR) results will be based on the final analysis described below.

Conditional power will be calculated using the following formula ([Mehta, 2010](#)):

$$CP(Z_1, \check{n}_2) = 1 - \Phi \left( \frac{Z_{\alpha} \sqrt{n_2} - Z_1 \sqrt{n_1}}{\sqrt{\check{n}_2}} - \frac{Z_1 \sqrt{\check{n}_2}}{\sqrt{n_1}} \right)$$

Where  $Z_1$  is the value of the Z score at the interim,  $n_1$  is the actual sample size at the interim,  $n_2$  is the total planned sample size (250 subjects), and  $\check{n}_2$  is the total planned sample size minus the actual sample size at the interim.

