13. STATISTICS

A full description of the statistical analyses to be performed at study completion will be provided in a Statistical Analysis Plan (SAP) prior to unblinding.

Baseline will be defined as those values recorded closest to, but prior to administration of the first dose of study drug.

Unless otherwise noted, significance tests of treatment differences will be tested at the two-sided 0.05 level.

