13.6. Interim Analyses

An interim analysis will be performed once approximately 50% of the planned patients have enrolled and those patients have either completed or discontinued the study. The purpose of the interim will be to potentially increase the sample size to maintain statistical power conditioned on the results of the first 50% of patients; or stop the study for futility if the conditional power is

sufficiently low. The study team will only be informed of the recommendation to maintain the original sample size, increase the sample size (by a fixed, pre-specified amount) or discontinue the study (at which point unblinding would occur).

For the primary and key secondary outcomes, the results from before and after the interim will be combined with Cui, Hung, Wang (CHW) methodology ([Cui, 1999](#)). Full details of the interim analysis procedure and steps to maintain treatment blinding of the study team will be described in the SAP and the IDMC Charter and finalized prior to execution of the interim analysis.

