## 5. SAMPLE SIZE DETERMINATION

The study is planned to enroll approximately 250 patients total in a 1:1 randomization, that is, 125 patients in each of the TNX-102 SL 5.6 mg and placebo arms. [REDACTED]

The interim analysis will re-evaluate these assumptions and the IDMC may recommend a sample size increase.

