## 12. CHANGES FROM PLANNED ANALYSIS

No changes from the protocol are planned at this time.

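### SAP 4.1 replaces the protocol's single fixed sample-size increase with a graded one, so any announced increase below +120 reveals the interim effect to the sponsor within a narrow band

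*SAP*

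**What the plan says.** Protocol 13.6 (repeated in the synopsis) confines the study team to three possible messages, of which the middle one is to "increase the sample size (by a fixed, pre-specified amount"). It leaves the steps that protect blinding to the SAP and the IDMC Charter.

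SAP 4.1 also begins by speaking of a fixed amount, but then sets a graded rule:

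- Conditional power under 20%: stop for futility.
- Conditional power 85% or more: no change.
- Anything between: "The increase will be chosen with the goal of increasing the sample size by the minimum number of subjects sufficient to raise the conditional power". The target is 90% or more, in steps of 10 and capped at 120. If 120 is not enough, the recommendation is 120.

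The recommendation goes to the sponsor, and the section adds: "No further information will be provided to the sponsor beyond this recommendation". The conditional power formula, thresholds, step size and cap all stand in the same section. SAP 12 states: "No changes from the protocol are planned at this time".

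**The concern.** The two documents describe different rules, and the SAP does not list the difference as a change. That needs reconciling in any case.

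The graded rule also has a consequence that the protocol's rule avoids. The increase is a deterministic, decreasing function of the interim Z, so its size carries information about the interim effect. The SAP contains no step that conceals the size or limits who receives it.

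The sponsor is the named recipient, and it has two documented ways to influence the second stage:

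- A sponsor medical monitor authorizes each patient for randomization (Protocol 10.1.4).
- The sponsor reviews new early terminations weekly with the CRO and challenges withdrawal reasons (SAP 7.1.3.1 and 7.1.3.2). Moving a patient from withdrawal of consent to lack of efficacy or adverse event changes the primary-analysis imputation from missing-at-random within arm to draws based on baseline values (SAP 9.1.1).

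The fixed-weight combination test protects the type I error against the change of sample size. It does not protect against altered patient selection or withdrawal coding.

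**Working it through.** The documents give no interim Z or table of increases, so there is no stated figure to reproduce. The check inverts the SAP's own rule.

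**Inputs.** Planned total 250 and 1:1 allocation (SAP 4.1 and 5). Interim n1 = 125, since the analysis comes "approximately 16 weeks after randomization of approximately 125 participants". Stage weights sqrt(0.5), fixed (SAP 9.1.1). Critical value 1.96, from the protocol's general statement that "significance tests of treatment differences will be tested at the two-sided 0.05 level". The level applied after an increase is redacted in SAP 7.1.1.2, so 1.96 is an assumption.

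**Zone limits.** At the planned size the SAP formula reduces to CP = Phi(2 Z1 - 1.96 sqrt(2)) = Phi(2 Z1 - 2.772).

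- CP = 20%: Z1 = (2.772 - 0.842)/2 = 0.965.
- CP = 85%: Z1 = (2.772 + 1.036)/2 = 1.904.

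**Graded steps.** With d extra patients and the fixed weights kept, CP = Phi(Z1 [1 + sqrt((125 + d)/125)] - 2.772). Setting this to 90% gives Z1 = (2.772 + 1.282)/[1 + sqrt((125 + d)/125)], with numerator 4.053 before rounding.

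- d = 30: 4.053/2.114 = 1.918, above 1.904, so +10 to +30 never occur.
- d = 60: 4.053/2.217 = 1.829.
- d = 70: 4.053/2.249 = 1.802.
- d = 110: 4.053/2.371 = 1.709.

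| Announced | Interim Z1 | CP at 250 |
|---|---|---|
| No change | 1.904 or more | 85% or more |
| +40 | 1.886-1.904 | 84.2-85.0% |
| +70 | 1.802-1.829 | 79.8-81.2% |
| +110 | 1.709-1.731 | 74.1-75.5% |
| +120 | 0.965-1.709 | 20-74.1% |

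Steps below +120 are 0.018 to 0.030 wide in Z1. With standardized difference = 2 Z1/sqrt(125), +70 gives 0.322 to 0.327 (two-sided p 0.067 to 0.071), whereas +120 gives only 0.173 to 0.306.

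**Other readings.** SAP 4.1 defines the second-stage n only for the planned size, so conditional power at an enlarged size is open to interpretation.

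- Enlarged second stage in both places of the printed formula: steps +30 to +110, each 0.03 to 0.05 wide; +120 is 0.965-1.573.
- Unweighted final test at the enlarged total: steps +50 to +110, each 0.007 to 0.024 wide; +120 is 0.965-1.765.
- Two-sided alpha of 0.04 or 0.03, or n1 of 115 or 135, shifts the limits by about 0.05 to 0.15. The widest step is then about 0.05.

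**How often.** Take Z1 as normal with mean delta sqrt(125)/2 and variance 1, under the fixed-weight reading.

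| True effect (SD) | P(+40 to +110) | P(+120) | Share of increases below +120 |
|---|---|---|---|
| 0.2 | 6.1% | 28.4% | 18% |
| 0.3 | 7.7% | 27.5% | 22% |
| 0.4 | 7.1% | 19.7% | 26% |

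For delta = 0.3 the mean is 1.677, and P(+40 to +110) = Phi(0.227) - Phi(0.032) = 0.077.

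**The case against.** The strongest case on the other side has five parts.

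1. *Most outcomes reveal little.* This stands. No change means only Z1 of 1.904 or more. About 74 to 82% of increases are +120, which leaves a wide band. A reader might infer that every announced target encodes the interim result one-to-one; that is true only below +120.
2. *The protocol's own rule leaks too.* This also stands. A single fixed increase reveals Z1 between 0.965 and 1.904. What the graded rule adds is mainly fine resolution between 1.71 and 1.90.
3. *Nobody is unblinded to treatment.* Correct. SAP 3.3 concerns study drug and treatment assignment, and no individual assignment can be deduced. What can leak is the aggregate effect.
4. *The no-further-information sentence is not false.* Correct. The size of the increase is part of the recommendation, so the sentence is literally true. The difficulty is how much the recommendation itself discloses.
5. *Site raters may never see the number.* A reader might infer that CAPS-5 and CGI-S raters are compromised. No passage shows that they receive the exact target or the formula. The IDMC Charter may govern this and is not available, so that route stays conditional. Neither document gives an accrual rate, so how much enrolment would follow the interim is unknown as well.

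The redacted critical value and the unspecified formula at enlarged sizes would hinder an outsider: +70 maps to non-overlapping bands under the three readings. They would not hinder a sponsor reader who knows both. None of these points removes the conflict between the documents or the disclosure to the sponsor below +120.

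**Conclusion.** The concern holds in limited form. SAP 4.1 departs from the protocol's single increase without declaring it. For increases below +120, it hands the sponsor the interim Z and aggregate effect within a band about 0.02 to 0.03 wide in Z1 (up to about 0.05 under other readings). Such a step has probability about 6 to 8% for true effects of 0.2 to 0.4 SD, or one increase in four to six. At +120 only Z1 of about 0.97 to 1.71 is learned.

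The exact limits rest on n1 = 125, a critical value of 1.96 and the fixed-weight reading; the pattern survived every alternative tried. The documents support a route to operational bias through the sponsor's authorization of randomization and its review of withdrawal reasons. They do not support saying that treatment blinding is broken or that site raters are exposed. The matter should be settled before the interim analysis.

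**What to change.** In SAP 4.1, restore the protocol's rule: one fixed, pre-specified increase of 120 (the SAP's existing maximum) whenever conditional power at the planned size is 20% to under 85%. An announced increase then reveals only Z1 of about 0.97 to 1.90. This needs SAP wording and a matching IDMC Charter.

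The cost falls in the 6 to 8% of cases where the graded rule would ask for 40 to 110. The trial then enrols 10 to 80 more patients than that rule requires. Weighting each shortfall (120 - d) by its probability gives an expected excess of 2.7 to 3.5 patients over true effects of 0.2 to 0.4 SD, so about three.

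If the graded rule is preferred, amend the protocol wording, list the change in SAP 12, and restrict the exact number to a named group walled off from eligibility authorization and withdrawal-reason review. Telling sponsor and sites only to continue would conflict with Protocol 13.6 and SAP 4.1 as written, so it could not be done through SAP and charter wording alone. Under such a restriction, those outside the group would have to plan supplies for up to 250 + 120 = 370 patients without knowing the target.

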2. SYNOPSIS

Name of Sponsor/Company: Tonix Pharmaceuticals, Inc.
Name of Investigational Product: TNX-102 SL (Cyclobenzaprine HCl Sublingual Tablets)
Name of Active Ingredient: Cyclobenzaprine HCl
Title of Study: A Phase 3, Double-Blind, Randomized, Multicenter, Placebo-Controlled Study to Evaluate the Efficacy and Safety of TNX-102 SL in Participants with PTSD Taken Daily at Bedtime (Protocol No. TNX-CY-P302)
Study center(s): Approximately 25-30 centers in the United States
Objectives: Primary: To evaluate the efficacy of TNX-102 SL (cyclobenzaprine HCl sublingual tablets) in the treatment of posttraumatic stress disorder (PTSD) Secondary: To evaluate the safety of TNX-102 SL (cyclobenzaprine HCl sublingual tablets) in the treatment of PTSD
Methodology: This is a 12-week, multicenter, randomized, double-blind, placebo-controlled, fixed-dose study that will investigate the efficacy and safety of TNX-102 SL 5.6 mg (2 x 2.8 mg tablets) – a sublingual formulation of cyclobenzaprine. Following successful screening and randomization, eligible patients will have a telephonic visit at Week 2 and then return to the study clinic for monthly visits at Week 4, Week 8, and Week 12 for assessments of efficacy and safety. There will be a total of 6 study visits over approximately 13-15 weeks of study participation, including Screening (Visit 1), Randomization (Day 1, Visit 2), a phone visit after 2 weeks of treatment and in-clinic visits after 4, 8, and 12 weeks of treatment. A total of approximately 250 patients will be randomized in a 1:1 ratio to placebo or TNX-102 SL 5.6 mg (2 x 2.8 mg tablets).
Number of patients (planned): Approximately 250 patients will be randomized. Randomized patients who withdraw will not be replaced.
Diagnosis and main criteria for inclusion: Inclusion criteria (assessed at Screening Visit 1): 
1. Male or female between 18 and 75 years of age, inclusive.2. Diagnosed with current PTSD as determined by the Clinician-Administered PTSD Scale (CAPS-5) for Diagnostic and Statistical Manual of Mental Disorders-Version 5 (DSM-5) and of sufficient symptom severity, defined as all of the following at Screening Visit 1 using the Diagnostic version (1-month recall):
a. The A criterion is 1=YES, and

- b. At least ONE item of the B criterion items must have a score of ≥ 2 , and
- c. At least ONE item of the C criterion items must have a score of ≥ 2 , and

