10.5.1. Early Termination (ET)

In accordance with the Declaration of Helsinki, patients have the right to withdraw from the study at any time for any reason, and they will be advised of this right. The investigator and Tonix also have the right to remove patients from the study. Specific reasons for removal of a patient from the study could include, but are not limited to:

- An adverse event (AE)
- An illness that, in the judgment of the investigator or Tonix, might invalidate the study results or place the patient at risk
- The request of the patient, investigator, or Tonix, whether for administrative or other reasons
- Pregnancy

This study will attempt to obtain as complete information as possible on all participating patients. An effort must be made to contact the medical monitor prior to any patient's early termination. Each reason for early termination will be adjudicated. Patients who wish to terminate their participation in the study should be instructed to come to the clinic for an Early Termination Visit. The purpose of the Early Termination visit is to obtain critical information about the patient's participation, and should be scheduled preferably before there has been a substantial lapse in study medication usage. However, even if there has been a medication lapse, the patient should be encouraged to return to the clinic for this visit, and should be instructed to return all study medication. NOTE: These visit procedures are not intended for patients who fail to qualify for randomization or for any other reason withdraw from the study prior to receipt of a dose of double-blind study drug.

If the patient withdraws prior to the Week 2 (Visit 3) visit window (before Day 11), the following assessments and procedures are to be completed at this visit in the following general order:

- Document reason for early termination. The investigator should carefully assess the role of adverse events and/or lack of efficacy when determining the most accurate reason for the patient's early termination.

- Collect study drug and assess compliance
- Assess occurrence of adverse events
- Update concomitant medications
- Obtain vital signs and weight
- Conduct urine pregnancy test (for women of child-bearing potential). Serum pregnancy test may be done at Investigator's discretion.
- Draw samples for clinical laboratory tests for:
 - Chemistry and hematology
- Perform visual examination of oral cavity

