#### 9.1.1 Primary Efficacy Analysis

An adaptive group sequential design will be performed for sample size adjustment or futility stop. To assure independence of the stage wise test statistics, the first stage population is defined as all participants available for efficacy analysis in the interim analysis. The second stage population is defined as all participants randomized after the interim cut-off and participants randomized prior to the interim cut-off, who were not available for efficacy analysis in the interim analysis.

Participants that drop out or reach Week 12 by the time of the interim cut-off will be included into the interim analysis. If the study continues until full planned recruitment, participants who were randomized prior to the interim cut-off, but did not drop out or reach Week 12 by the time of the interim cut-off, will be included into the second stage test statistic. Participants that were randomized after the interim cut-off will be included in the calculation of the second stage test statistic. Note that in every case, only participants that meet the mITT population criteria will be included.

Data of different stages will be combined using the inverse normal method to test the null hypotheses that there is no difference in the change from baseline in CAPS-5 total score between TNX-102 SL and placebo treatment groups at Week 12 ([Cui 1999](#)):

$$Z_1 = \Phi^{-1}(1 - p_1)$$

and  $Z_2 = w_1 Z_1 + w_2 \Phi^{-1}(1 - p_2)$

Where:

$Z_1$ = the Z statistic for the first stage

$Z_2$ = the combination test statistic at the end of the second stage

$w_i$ = the weighting applied for each associated Z statistic

$p_1$ = the first stage p-value

$p_2$ =the second stage p-value based on second stage participants

For maximum statistical efficiency, the weights are defined prospectively according to the square-root of the planned proportion of participants in the two stages, relative to the preplanned total enrollment of 250 participants, as  $w_i = \sqrt{0.5}$ . The calculation of these

weights is fixed and will not be changed due to unblinded data and is hence in line with the draft guidance on adaptive design clinical trials ([CDER, CBER, February 2010](#)). In order to control the type-I error, adaptive changes of the stage wise sample sizes will not lead to changes of the weights ([Lehmacher & Wassmer 1999](#)).

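### The conditional-power formula sets a randomized total of 250 against an interim count whose population is not named; if that count is mITT, conditional power is overstated by up to about 5 points at 10% loss

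*SAP*

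**What the plan says.** SAP 4.1 gives a conditional-power formula with three sample-size terms. Of n1 it says that it "is the actual sample size at the interim", with no population named. Of n2 it says that it "is the total planned sample size (250 subjects". The third term, the remaining sample, is the difference between the two.

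The 250 is a count of randomized patients. The protocol synopsis states "Approximately 250 patients will be randomized. Randomized patients who withdraw will not be replaced", and SAP 5 has "The study is planned to enroll approximately 250 patients total in a 1:1 randomization".

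The test statistics rest on a smaller set. In SAP 9.1.1, "the first stage population is defined as all participants available for efficacy analysis in the interim analysis", and for both stages "only participants that meet the mITT population criteria will be included". SAP 6 requires a baseline and at least one post-baseline CAPS-5 for mITT. Protocol 10.5.1 has a separate early-termination list that begins "If the patient withdraws prior to the Week 2 (Visit 3) visit window (before Day 11", and that list contains no CAPS-5. The list for later withdrawals does contain one. SAP 9.1.1 then combines the stages with weights fixed at √0.5 each.

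SAP 4.1 describes the interim trigger in two ways: as about half of the planned 250 being evaluable for efficacy, and as about 16 weeks after some 125 participants have been randomized. It stops for futility below 20% conditional power, increases the sample from 20% to below 85%, and leaves the size unchanged at 85% or above.

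**The concern.** Z1 comes from mITT patients, so the natural reading of n1 is the number of mITT patients behind it. On that reading the formula subtracts an analysed count from a randomized total. The difference counts patients who will be randomized but not analysed, and the stage-2 information in the formula will not be reached.

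There is a second mismatch. The formula weights the stages by n1/n2, whereas the final test uses √0.5 for each. The two agree at n2 = 250 only when n1 = 125.

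Conditional power alone selects among three recommendations. An overstated value lets some trials that lie below the plan's own 20% line receive an increase instead of a futility stop. It also tells some trials that lie below 85% that no increase is needed, and where an increase is made it tends to make it too small.

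**Working it through.** **Inputs.** n2 = 250 (SAP 4.1). Weights w1 = w2 = √0.5 (SAP 9.1.1). Lines at 20% and 85% (SAP 4.1). Zα = 1.96 is an assumption taken from the two-sided 0.05 level in protocol 13; SAP 4.1 gives no value, and the level after an increase is redacted. L, the share of randomized patients who never enter mITT, is not given in the visible text; I assume 2%, 5% and 10%.

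**The plan's own figures.** The stage weights reproduce: √(125/250) = √0.5 = 0.7071. The SAP states no numerical conditional power to check.

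**Formulas.** With r = n2 − n1, the SAP formula is CP = 1 − Φ(A), where

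A = Zα·√(n2/r) − Z1·[√(n1/r) + √(r/n1)].

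For the test actually used, with m2 analysed stage-2 patients, CP = 1 − Φ(A*), where

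A* = (Zα − w1·Z1)/w2 − Z1·√(m2/n1) = 2.772 − Z1·[1 + √(m2/n1)].

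With no loss and n1 = 125, both reduce to 2.772 − 2·Z1. The lines then sit at Z1 = (2.772 − 0.842)/2 = 0.965 for 20% and (2.772 + 1.036)/2 = 1.904 for 85%.

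**Case 1: 125 randomized at the interim, n1 = mITT count, L = 10%.**
- n1 = 112.5 and r = 137.5, so A = 2.643 − 2.010·Z1. The SAP formula reads 20% at Z1 = 0.896 and 85% at Z1 = 1.830.
- The analysed stage-2 number is m2 = 225 − 112.5 = 112.5, so A* = 2.772 − 2·Z1.
- At Z1 = 0.896, A* = 0.980 and CP = 16.4%. At Z1 = 1.830, A* = −0.889 and CP = 81.3%.
- Affected Z1 bands: about 0.90–0.97 and 1.83–1.90.

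**Case 2: 125 mITT at the interim, L = 10%.**
- The SAP lines stay at 0.965 and 1.904.
- m2 = 225 − 125 = 100, so A* = 2.772 − 1.894·Z1.
- At 0.965, CP = 17.3%. At 1.904, CP = 79.8%. The lines for the test actually used are at about 1.02 and 2.01.
- Affected Z1 bands: about 0.97–1.02 and 1.90–2.01.
- Separating the two effects: changing only n2 to 225 and keeping the n1/n2 weighting gives 15.9% / 81.4%. Using the fixed weights as well gives 17.3% / 79.8%. In Case 1 the weights make no further difference, because 112.5/225 = 0.5.

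**What a computed 20% / 85% corresponds to**

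| L | 125 randomized at interim | 125 mITT at interim |
|---|---|---|
| 2% | 19.2% / 84.3% | 19.5% / 84.1% |
| 5% | 18.1% / 83.3% | 18.6% / 82.6% |
| 10% | 16.4% / 81.3% | 17.3% / 79.8% |

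**Case 3: n1 and n2 both randomized, equal loss in the two stages.** A depends only on Z1 and n1/n2, so multiplying both counts by (1 − L) changes nothing. At Z1 = 1.2 and n1/n2 = 0.5, CP is 35.5% for L = 0, 5%, 10% or 20%.

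**Sensitivity to Zα.** With a one-sided 5% critical value, Case 1 at L = 10% gives 16.9% / 81.9%, so the direction and approximate size hold.

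**How often it matters.** In Case 1 at L = 10%, with Z1 normal with unit SD and mean 0, 1.0 or 1.98, the chance of landing in either single band is at most about 3%.

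**The case against.** The strongest reply is that SAP 4.1 never says n1 is the mITT count. One of its trigger wordings counts randomized participants, and two randomized counts with equal loss give no bias at all. That stands. A reader might infer that the formula is an established arithmetic error, and the text does not support that: the formula is sound when its counts share a scale. The mITT reading is an inference from SAP 9.1.1, although the more natural one.

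A reader might also take a fixed band, such as Z1 from 1.90 to 2.01, as the set of trials wrongly denied an increase. That band needs 125 mITT patients at the interim and 10% loss. At 10% loss, 125 mITT means about 125/0.9 = 139 randomized. If 125 are randomized instead, the band is 1.83–1.90, and from 1.904 upward conditional power is at or above 85%.

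The loss rate is unknown. Early-termination visits from Day 11 onward include a CAPS-5, so loss from mITT may be small; patients who never return add to it by an unknown amount. The sample-size assumptions are redacted and may contain an attrition allowance. The protocol also refers interim details to the IDMC Charter, which is not available here.

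Finally, the corrected figures are themselves approximations. Both formulas project the observed trend forward, and under MMRM with multiple imputation a headcount is only a proxy for information. Z1 has a standard error of about 1, against line shifts of about 0.05 to 0.11 at 10% loss. This limits the size of the concern but does not justify mixing the two scales.

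**Conclusion.** The point holds conditionally. If n1 is the mITT count behind Z1, using 250 as n2 overstates conditional power at both lines, under either trigger wording. With Zα = 1.96, the overstatement is about half a point to one point at 2% loss, about 1.4 to 2.4 points at 5%, and about 3 to 5 points at 10%. If n1 and n2 are both randomized counts and loss is equal across the stages, it is zero.

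A reader might infer that the false-positive rate is at risk. It is not, under any reading, because the combination weights are fixed in advance. What is affected is whether the futility and sample-size rules act at the values the SAP states, and only for Z1 in narrow bands. It is still worth correcting: n2 = 250 is a stated input, not merely a missing detail, and the formula's stage weights match the final test only at n1 = 125.

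**What to change.** In SAP 4.1:

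- Define n1 as the number of mITT participants in the interim analysis.
- Replace the remaining sample by the expected stage-2 mITT number, m2 = (250 + any increase) × (blinded pooled mITT fraction at the interim) − n1.
- Compute conditional power for the test that will be run: CP = 1 − Φ[(Zα − w1·Z1)/w2 − Z1·√(m2/n1)], with w1 = w2 = √0.5, and state Zα.
- Reconcile the two trigger descriptions (about 125 evaluable versus about 125 randomized).

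The cost is a short redefinition in one section, and no new data are needed. Where n1 is an mITT count, computed conditional power becomes slightly less favourable, so futility stops and sample-size increases become slightly more likely.

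### SAP 4.1 does not define conditional power at an enlarged second stage, and the obvious substitution into its formula picks too small an increase for the fixed-weight final test

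*SAP*

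**What the plan says.** SAP 4.1 stops the trial for futility below 20% CP and makes no increase "If the conditional power is at or over 85% with the current sample size". Between those limits the sample size is to be raised "by the minimum number of subjects sufficient to raise the conditional power to at least 90" percent, and "the maximum increase will be limited to 120 additional participants in blocks of 10 participants". If even 120 more patients fall short of 90%, the recommendation is 120.

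The only CP expression is written as a function of Z1 and ň2. The definitions beneath it say that n1 "is the actual sample size at the interim", that n2 is the planned total of 250, and that ň2 "is the total planned sample size minus the actual sample size at the interim". Zα is not defined there. The interim is timed "approximately 16 weeks after randomization of approximately 125 participants".

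SAP 9.1.1 combines the two stages by the inverse normal method with both weights equal to √0.5. These come from the planned halves of 250 and stay the same after an increase.

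**The concern.** Finding the smallest sufficient increase means computing CP at +10, +20 and so on, but the definitions stop at the planned size. The user has to decide what to substitute.

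The choice matters because ň2 appears twice. In the first term it scales the critical value, which under fixed weights must not change. In the second it scales the drift expected from the new patients, which must grow. No single value does both jobs. Two competent statisticians could therefore recommend different increases from the same interim result, and one of them could report 90% when the planned test has less.

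A related mismatch affects the 20% and 85% limits: the formula uses the actual interim size, while the final weights assume it was exactly half of 250.

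**Working it through.** **Inputs.** n2 = 250, the 20%, 85% and 90% levels, the cap of 120 and the blocks of 10 are from SAP 4.1. The weights √0.5 are from SAP 9.1.1. zα = 1.960 is assumed from the general two-sided 0.05 rule in Protocol 13, because the level after an increase is redacted in SAP 7.1.1.2. n1 = 125 unless stated. The plan gives no worked CP or increase to reproduce.

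**CP of the planned test.** The final statistic is √0.5·Z1 + √0.5·Z(2), where Z(2) is the second-stage statistic. If the observed trend continues, Z(2) has mean Z1·√(m/n1) for m second-stage patients. Hence

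CP(m) = 1 − Φ[(zα − √0.5·Z1)/√0.5 − Z1·√(m/n1)].

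With n1 = 125 and m = 125 this equals the SAP formula: both first terms are 1.960·√2 − Z1. The 20% and 85% limits then fall at Z1 = 0.965 and 1.904.

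**Three ways to enter an increase d:**
- A, fixed-weight: first term unchanged, drift uses 125 + d.
- B: ň2 = 125 + d in both places, n2 = 250.
- C: ň2 = 125 + d and n2 = 250 + d.

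**Worked case, Z1 = 1.80.** The first term is 2.772 − 1.80 = 0.972.
- Current size: Φ(1.80 − 0.972) = 79.6%.
- A, +70: drift 1.80·√(195/125) = 2.248, CP Φ(1.276) = 89.9%. A, +80: drift 1.80·√(205/125) = 2.305, CP Φ(1.333) = 90.9%. The increase is +80.
- B, +50: first term (1.960·√250 − 1.80·√125)/√175 = 0.821, drift 1.80·√(175/125) = 2.130, displayed CP Φ(1.308) = 90.5%. The final test has Φ(2.130 − 0.972) = 87.7%.
- C, +100: first term (1.960·√350 − 1.80·√125)/√225 = 1.103, drift 1.80·√(225/125) = 2.415, displayed CP Φ(1.312) = 90.5%. The final test has Φ(2.415 − 0.972) = 92.6%.

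| Z1 | CP at 250 | A (true CP) | B (displayed; true CP) | C (true CP) |
|---|---|---|---|---|
| 1.75 | 76.7% | +100 (90.8%) | +60 (90.1%; 86.6%) | +120 (92.3%) |
| 1.80 | 79.6% | +80 (90.9%) | +50 (90.5%; 87.7%) | +100 (92.6%) |
| 1.85 | 82.3% | +60 (90.8%) | +40 (90.7%; 88.6%) | +80 (92.6%) |
| 1.90 | 84.8% | +40 (90.5%) | +30 (90.9%; 89.3%) | +50 (91.6%) |

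Simulating the weighted test agreed with these true values within 0.1 point.

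**Where the readings part.**
- Below about Z1 = 1.57 all three give +120.
- From there to about 1.689, no permitted increase gives the final test 90%. A and C go to the cap; B stops earlier.
- From about 1.689 upwards 90% is attainable. B is worst near Z1 = 1.708: +70 against +120, true CP 85.8%.

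**Sensitivity to the level.** At two-sided 0.04 and Z1 = 1.80 the increases are +100 / +60 (true CP 86.1%) / +120.

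**Interim size other than 125.** At n1 = 145 the printed formula reaches 85% at Z1 = 2.004. The fixed-weight CP there has first term 2.772 − 2.004 = 0.768 and drift 2.004·√(105/145) = 1.705, so Φ(0.938) = 82.6%. Its own 85% point is 2.057. At n1 = 115 the printed limits are 0.910 and 1.846, against 0.926 and 1.828.

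**Across trials.** Planning power is redacted, so 80% and 90% are assumed, with Z1 normal about (1.960 + z_power)·√0.5 and SD 1. B misses an attainable 90% in 8.4% and 7.6% of trials. Overall power under A / B / C is 79.5 / 79.2 / 79.6% and 88.6 / 88.4 / 88.6%.

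**The case against.** The strongest reply is that the right reading can be inferred. SAP 9.1.1 fixes the weights, Protocol 13.6 names the same combination method, and a statistician computing CP for that test arrives at A. That is fair, but SAP 4.1 does not point to 9.1.1, and its formula yields A only if its two ň2 terms are treated differently.

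The IDMC Charter is not among the documents, and SAP 4.1 cites a methods paper for the formula. Either may contain the rule. The formula was also read from a PDF, and an accent could have been lost. The definitions list only n1, n2 and ň2 as sample sizes, so a separate symbol for an enlarged stage would still be undefined in the SAP.

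Three stronger readings do not stand.
- A reader might infer that CP can never move, so that every result from 20% to below 85% leads to +120. SAP 4.1 speaks of raising CP by adding patients and of increases that fall short, so an enlarged value is plainly intended.
- A reader might count every case in which B ends below 90%, which is 11–13% of trials with true CP down to 83.1%. About a third of these are cases where +120 itself cannot reach 90%, and SAP 4.1 provides for that.
- A reader might see a contradiction between the blocks of 10 and the instruction to "recommend to the Sponsor to increase the sample size by a fixed amount". Protocol 7.2 refers to Section 13.2 for the adjustment, and most of that section is redacted, so no contradiction is shown.

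**Conclusion.** The point holds as a moderate correction. SAP 4.1 does not say how to compute CP at an enlarged second stage. Enlarging ň2 wherever it is printed gives the wrong CP for the final test and up to 50 patients too few (70 against 120). Enlarging n2 as well errs the other way, by up to 30 patients (120 against 90, near Z1 = 1.754). The printed limits match the final test only at n1 = 125. That mismatch is minor: at n1 = 145 the two versions of the 85% limit disagree in about 2% of trials.

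Nothing here supports a claim of inflated type I error, since the fixed weights protect it. Overall power changes by less than half a point. What is at stake is whether the IDMC recommendation can be reproduced and whether the SAP's own 90% target is met when it is reported as met.

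The figures rest on zα = 1.960, n1 = 125 where not stated otherwise and, for the trial-level rates, an assumed planning power of 80% to 90%.

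**What to change.** Before the interim, state in SAP 4.1:

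CP(m) = 1 − Φ[(zα − w1·Z1)/w2 − Z1·√(m/n1)], with w1 = w2 = √0.5, n1 the actual interim size and m = 250 + candidate increase − n1.

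Give the value of zα. Use this one formula for the 20% limit, the 85% limit and the choice of increase, and refer to SAP 9.1.1 for the weights. A one-line example would settle the reading: two-sided 0.05, n1 = 125, Z1 = 1.80, CP 79.6% at 250, increase +80, CP 90.9%.

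If the IDMC Charter or the cited methods source already gives this rule, copy it into SAP 4.1. The cost is SAP wording only: the cap, the final test and its weights stay as they are.
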